Combination Entecavir and Peginterferon alfa-2a Therapy in HBeAg-Positive Immune Tolerant Adults with Chronic Hepatitis B

Synopsis

Study aims:

- To determine the safety and efficacy of treatment with 8 weeks of entecavir followed by 40 weeks of both entecavir and peginterferon alfa-2a in the treatment of chronic hepatitis B in HBeAg positive adults who are in the immune tolerant phase.
- To evaluate “off treatment” sustained responses after treatment with entecavir and peginterferon alfa-2a in the treatment of chronic hepatitis B in HBeAg positive adults who are in the immune tolerant phase.

Type of study

- Single arm treatment study

Clinical trial

A single arm pilot study of 8 weeks of entecavir followed by 40 weeks of both entecavir and peginterferon alfa-2a in adults with HBeAg-positive chronic hepatitis B with normal or near normal ALT levels and high serum levels of HBV DNA (“immune tolerant” HBeAg-positive chronic hepatitis B). All participants will be followed until week 96 (48 weeks after discontinuation of therapy) at which time the primary outcome will be measured.

1. Background

1.1. “Immune tolerant” HBV in adults

Chronic hepatitis B virus infection (CHB) affects 360 million people worldwide, including approximately 2.0 million in North America. Chronic hepatitis B may result in progressive liver disease that leads to cirrhosis, end-stage liver disease and hepatocellular carcinoma (HCC). Indications and approaches to therapy of hepatitis B are based upon knowledge of the features of its natural history. The natural history of chronic hepatitis B, particularly if acquired in early childhood, runs through several stages or phases that have different clinical manifestations and implications for long-term hepatic injury (1, 2). The initial “immune tolerant” phase is variable in duration, but typically evolves during childhood or early adulthood to the “immune clearance” phase, marked by rises in serum alanine aminotransferase (ALT) and aspartate aminotransferase (AST), increased inflammation and hepatocellular necrosis on liver biopsy, and an increase in cytoplasmic hepatitis B core antigen (HBcAg) expression. As the term ‘immune tolerant’ (IT) suggests this is a state where the host appears to exert no overt immune response to a chronic infection with Hepatitis B. The state is characterized by the presence of hepatitis B e antigen (HBeAg) and high levels of hepatitis B virus (HBV) DNA (typically HBV DNA $\geq 10^8$ IU/mL), but minimal or no elevations in serum ALT and AST levels and minimal activity or injury on liver biopsy. Most but not all individuals with ‘Immune Tolerant’ CHB are children or young adults, with a mean age of transition to the immune clearance phase of ~30 years. Thus, many adults with CHB who acquired their infection at birth or in early childhood may be in the immune tolerant phase of the infection up to the age of 30 or 40 years, or longer.

Adults in the immune tolerant CHB phase have variable histologic findings, largely dependent upon the definition of ALT used to define the population. For studies using the more stringent ALT criteria of ≤ 30 U/L for males and ≤ 19 U/L for females, histologic disease is minimal (majority fibrosis $<2/4$ and necroinflammation 0-1/4) (3-5). Natural history studies of adults in the immune tolerant phase have shown that the ALT levels were significantly higher in patients with

subsequent loss of tolerance. For inclusion criterion, we propose to use ALT upper limits of 30 U/L for females and 45 U/L for males, and avoid the need for liver biopsy.

It has been hypothesized that the mother-to-child HBV transmission leads to transplacental transfer of maternal HBeAg that may induce a specific unresponsiveness of helper T cells to HBeAg in neonates. Because HBeAg and HBcAg are highly cross-reactive at the T-cell level, deletion of the helper T-cell response to HBeAg results in an ineffective cytotoxic T-lymphocyte response to HBcAg (6). During the immune tolerant phase of chronic infection, the continued secretion of HBeAg (the tolerogen) is necessary to maintain the tolerant state. Little is known about the mechanisms that regulate the loss of immune tolerance in chronic HBV infection. Recent studies have emphasized the importance of low expression of transporter associated with antigen processing (TAP1) and low molecular weight protein 2 (LMP2) compared with CHB patients in the immune clearance phase, suggesting a deficiency in antigen processing and transport to major histocompatibility complex class I molecules in IT adults (7). Point mutations and deletions in HBV epitopes that occur prior to or concurrent with the onset of the immunoactive phase during chronic HBV infection may contribute to a significant decrease in both viral replicative competence and HBV-specific CD8(+) T cell responses, and in turn, lead to maintenance of viral persistence (8). The proposed study will provide an opportunity to study the immunologic features and correlates of immune tolerant HBV infection in adults as well as the immune markers associated with breaking of tolerance in the context of antiviral therapy.

1.2 Treatment of CHB in adults

The known natural history of chronic hepatitis B underlies the current criteria for therapy and the endpoints of treatment. Treatment of adults with CHB targets those with active disease, characterized by elevated ALT levels and/or evidence of significant inflammatory activity or fibrosis on biopsy in conjunction with elevated HBV DNA levels. Treatment of adults in the immune tolerant phase of infection is not recommended (9). Reasons for not recommending treatment include the low frequency of histologic disease and complications and the lack of established effective therapies. Serum HBV DNA level has been found to be directly correlated with the development of HCC and cirrhosis independent of serum ALT level, HBV genotype, and HBeAg status (10,11). This has led to promotion of the use of serum HBV DNA concentration as an indicator for treatment regardless of serum ALT level, and even patients with normal serum ALT levels are to be treated with antiviral therapy with the primary aim of suppressing HBV DNA. In this context, the risks and benefits of treatment of immune tolerant adults is an important issue – not addressed by treatment studies to date.

Currently, there are two broad categories of HBV therapies available: pegylated interferon (peginterferon) and nucleos(t)ide analogues. The advantages of nucleos(t)ide analogue therapy is the ease of administration, the lack of significant side effects and the consistent suppression of HBV DNA that can be achieved, particularly with the newer agents such as tenofovir and entecavir. While emergence of drug resistance can limit the efficacy of oral agents, entecavir and tenofovir are characterized by great potency and higher genetic barrier to resistance leading to a low rate of antiviral resistance (1% or less even with prolonged therapy for 4 to 5 years). As a consequence, 80-90% of patients treated long-term with these agents achieve rates of marked suppression of HBV DNA levels and normal ALT levels. The advantage of peginterferon therapy is that it is administered for a limited period (6 to 12 months) and results in loss of HBsAg in a significant proportion of patients. The latter feature may be particularly relevant in the treatment of immune tolerant adults, the target population for this study. Previous studies have shown that a one-year course of combination therapy of peginterferon and nucleos(t)ide analogue does not yield a higher response rate than a one-year course of either agent alone. However, these studies have been limited by the use of a nucleos(t)ide analogue

with high risk of resistance (e.g. lamivudine) and may have been affected by the concurrent use of peginterferon and nucleos(t)ide analogue rather than sequential use.

1.3 Considerations in the treatment of immune-tolerant adults

There are no prior studies of treatment of immune tolerant adults. Data from the pediatric literature indicated that treatment with IFN alone during the immune tolerant phase of infection is rarely effective and loss of HBV DNA or anti-HBe seroconversion, with less than 10% of treated children achieving this outcome (12). However, the combination of a nucleoside analogue and IFN was examined in a pilot study of 23 children and appears encouraging (13). Lamivudine was given for 8 weeks and then combined IFN and lamivudine therapy for a further 44 weeks. HBV DNA by PCR was negative in 48% at end of treatment, and 5 (22%) children seroconverted to anti-HBe. Four (17%) children cleared HBsAg and seroconverted to anti-HBs. Six months after treatment, HBV DNA was again positive in all but the children who had seroconverted to anti-HBe and (presumably) anti-HBs.

Based upon these stimulating results, we propose to evaluate the safety and efficacy of a short lead-in course (8 weeks) of entecavir followed by combination of entecavir plus peginterferon alfa-2a for 40 weeks. We hypothesize that using a potent nucleos(t)ide analogue will provide a higher rate of HBeAg loss and suppression of HBV DNA. The primary measure of outcome will be HBeAg loss and suppression of HBV DNA to ≤ 1000 IU/mL in serum 48 weeks after stopping all antiviral therapy (sustained off-treatment response).

2. Study objectives

2.1 Primary objectives

- To determine the safety and efficacy of treatment with 8 weeks of entecavir followed by 40 weeks of both entecavir and peginterferon alfa-2a in the treatment of chronic hepatitis B in HBeAg positive adults who are in the immune tolerant phase.
- To evaluate “off treatment” safety and sustained responses after treatment with entecavir and peginterferon alfa-2a in the treatment of chronic hepatitis B in HBeAg positive adults who are in the immune tolerant phase.

2.2 Primary endpoint

2.2.1 Safety: Adverse Events and Serious Adverse Events through the end of treatment and through the end of follow-up

2.2.2 Efficacy: HBeAg loss (lack of detectable HBeAg) AND HBV DNA $\leq 1,000$ IU/mL 48 weeks after stopping therapy.

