6.5 End of treatment assessment

At week 48, all participants will complete the treatment phase. Laboratory testing will be performed as outlined in Appendix 1 Schedule of Events. A sample of blood will be stored for eventual assessment of HBeAg and HBsAg concentration.

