6.9. Management of non-response

Definition: Primary non-response is defined as a failure to achieve at least $>1\text{-log}_{10}$ IU/mL decline in HBV DNA after the first 24 weeks of treatment by the quantitative HBV DNA assay, which will be confirmed on re-testing 4 weeks later. Compliance with study medications will be assessed and documented. Primary non-response is considered treatment failure. In the event of non-response, the following will be implemented:

6.9.1. Reinforce compliance upon initial determination of non-response.

6.9.2. Treatment (both entecavir and peginterferon alfa-2a) will be discontinued if non-response is confirmed on re-testing 4 weeks later.

6.9.3. Participants will be assessed at week 4 after treatment discontinuation and then be followed at weeks 12, 24, and 48 post-discontinuation .

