6.10. Management of virological breakthrough

Definition: Virological breakthrough is defined as a $> 1\text{-log}_{10}$ IU/mL increase in HBV DNA level from nadir in a participant with an initial virological response or redetection of HBV DNA after becoming undetectable, and will be confirmed on re-testing 4 weeks later in a participant with either an initial or partial virological response and who has been compliant with study medications.

- Virologic breakthrough is considered a treatment failure.

Management algorithm if virological breakthrough
6.10.1. Reinforce compliance. The importance of compliance with study medication will be reinforced with study participants at each visit.

6.10.2. Resistance testing will be performed but will not be used to guide decisions (as results will not be available in real-time). Participants meeting the definition for virologic breakthrough on repeat testing will stop all treatment.

6.10.3. Participants will be assessed at weeks 4, 12, 24, and 48 post-discontinuation.

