8.1.1. Analysis of primary endpoints

The primary endpoints include safety, measured by the rate of adverse and Serious Adverse Events, and efficacy, defined as loss of HBeAg and HBV DNA $\leq 1,000$ IU/mL at the end of follow-up (week 96). That is, only participants achieving HBeAg loss and having HBV DNA ≤ 1000 IU/mL at the end of follow-up will be considered as achieving the primary efficacy endpoint.

Safety

Summaries of adverse events (number of adverse events, number and percentage of participants with at least one adverse event, and for each adverse event, rate per person-years) will be provided. Events will be summarized based on the date of onset for the event. A treatment emergent adverse event will be defined as an adverse event that begins on or after the date of first dose of study drug.

Summaries of the following are planned:

- all adverse events recorded between screening and first dose of study medication,
- all treatment emergent adverse events,
- all emergent and related adverse events,
- all treatment emergent renal adverse events,
- all treatment emergent and related renal adverse events
- combined Grade 2, 3 and 4 treatment emergent adverse events,
- combined Grade 2, 3 and 4 related treatment and emergent adverse events,
- combined Grade 3 and 4 treatment emergent adverse events,
- combined Grade 3 and 4 related treatment and emergent adverse events,
- all adverse events that caused permanent discontinuation of study drug,
- all adverse events that caused temporary interruption of study drug,
- all serious adverse events, and
- all serious and related adverse events.

We will provide 95% confidence intervals for the rate of adverse and serious adverse events.

Efficacy

The percentage of participants achieving the primary efficacy endpoint will be summarized with the point estimate and 95% confidence interval.

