8.2. Missing data

Primary analyses will be performed using all enrolled participants (intention-to-treat analysis). Participants who do not have primary endpoint data due to drop-out or other reasons at the end of follow-up will be considered as treatment failures. Since this is a pilot study with a small sample size, formal procedures for handling missing data such as inverse-weighting and multiple imputation will not have enough power, nevertheless, we will apply the following methods to assess the sensitivity of our primary analysis results to different missing data assumptions:

1. Single LOCF Imputation: In this case the primary endpoint analysis will be repeated by replacing missing endpoint data at follow-up using data from prior visits.
2. Inverse-probability-weighting: This analysis will be carried out in two stages. In the first stage, for each subject we will estimate the probability of having complete data at week 96 based on the data collected at prior visits using logistic regression. In the second stage, the primary endpoint analyses will be repeated by weighting each subject with complete data by the inverse of the corresponding estimated probability from the first stage.
3. Multiple Imputations: The missing values at week 96 will be imputed by Markov-Chain Monte-Carlo algorithm, based on the data collected prior to week 96. Five such imputations will be used and the results of the primary endpoints analyses will be repeated on each of these imputed datasets and averaged.

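### The primary endpoint has two time anchors, 48 weeks after stopping therapy and week 96, and no rule says which applies to participants who stop all therapy early

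*Combined protocol and SAP*

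**What the plan says.** **Anchor A, counted from stopping.** Section 2.2.2 requires HBeAg loss and HBV DNA at or below 1,000 "IU/mL 48 weeks after stopping therapy". Section 1.3 gives the same clock: "in serum 48 weeks after stopping all antiviral therapy (sustained off-treatment response".

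**Anchor B, the study calendar.** Section 8.1.1 defines the same endpoint as HBV DNA at or below 1,000 "IU/mL at the end of follow-up (week 96"), together with HBeAg loss. Section 8.3 uses this wording for the precision calculation. In section 8.2 the weighting analysis will "estimate the probability of having complete data at week 96", and the multiple imputation fills in week-96 values.

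**Text that equates the two.** The synopsis states: "All participants will be followed until week 96 (48 weeks after discontinuation of therapy) at which time the primary outcome will be measured". Section 6.5 adds: "At week 48, all participants will complete the treatment phase".

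**Text that separates them.** Section 6.8 lists reasons for stopping therapy early. After confirmed non-response, section 6.9.3 has participants seen 4 weeks after stopping and then "be followed at weeks 12, 24, and 48 post-discontinuation". Section 6.10.3 gives the same four time points after breakthrough. Neither section lists a week-96 visit. Section 6.9 classes primary non-response as a treatment failure, and section 6.10 says the same of breakthrough: "Virologic breakthrough is considered a treatment failure".

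**The concern.** The trial's main efficacy output is one proportion and its interval in 40 participants, so the endpoint needs one time point. For anyone who stops all therapy before week 48, sections 2.2.2 and 8.1.1 name different dates, and the plan does not say which visit supplies the result.

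There are two consequences. First, section 8.2 does not carry over the failure status set in 6.9 and 6.10. A participant already declared a failure, but with no week-96 visit, would be dropped from the weighted analysis and have an outcome imputed in the multiple-imputation analysis. Both treatments can raise the estimate. Secondly, for participants who stop for other reasons, the choice of anchor can decide whether they count as responders in the primary analysis.

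**Working it through.** **1. The plan's own figure.** Section 8.3 takes n = 40 and an expected proportion of 25%, so x = 10. The Clopper-Pearson limits are the 2.5% quantile of Beta(10, 31) and the 97.5% quantile of Beta(11, 30): 0.127 and 0.412, width 0.285. The plan prints 0.127, 0.412 and 0.29, so the row reproduces. It is the base case below.

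**2. When the anchors part.** If all therapy stops at week S, anchor A falls at S + 48 and anchor B at 96. The gap is 96 − (S + 48) = 48 − S weeks.

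| Stop week S | S + 48 | Gap to week 96 |
|---|---|---|
| 28 (non-response at week 24, confirmed 4 weeks later) | 76 | 20 |
| 36 | 84 | 12 |
| 42 | 90 | 6 |
| 48 | 96 | 0 |

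The standard post-treatment visits in section 6.6 (weeks 52, 60, 72, 96) lie 4, 12, 24 and 48 weeks after week 48. Sections 6.9.3 and 6.10.3 use the same four intervals, counted from the stopping date.

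**3. What the documents give for each stopping reason.**

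| Reason | Follow-up stated | Status |
|---|---|---|
| Non-response, breakthrough (6.9, 6.10) | To 48 weeks after stopping; no week-96 visit listed | Declared failures |
| Grade IV toxicity, decompensation (6.8) | Post-treatment schedule, until resolved or stabilized; clock not stated | Open |
| ALT flare (6.11.3) | Remain in the study; clock not stated | Open |
| Refusal, pregnancy (6.8) | No efficacy visit schedule | Open |
| One drug stopped for an adverse event (7.5.4) | Other drug continues to the end of treatment | Anchors coincide |

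**4. Non-response and breakthrough stoppers in each analysis.**
- *Primary analysis.* They are failures under 6.9 and 6.10, and absent end-of-follow-up data also count as failure under 8.2. Shift: 0.
- *LOCF.* The last visit of a week-28 stopper is week 76, exactly 48 weeks after stopping. The measured result would probably be a failure.
- *Weighting.* If the schedule ends before week 96, this group has no scheduled chance of complete data, so it drops out. Suppose 10 responders of 40 (25.0%) and m such stoppers (m is an assumption). With no outcome information in the weights, the estimate is 10/(40 − m): m = 1, 10/39 = 25.6%; m = 2, 10/38 = 26.3%; m = 4, 10/36 = 27.8%; m = 8, 10/32 = 31.3%. These are unweighted complete-case figures. If instead earlier HBV DNA separates responders from non-responders, then with m = 4 the 26 observed non-responders each carry weight 30/26, and the estimate is 10/(10 + 26 × 30/26) = 10/40 = 25.0%.
- *Multiple imputation.* It also draws on data before week 96. Some declared failures could be imputed as responders; how many depends on the model.

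**5. Other early stoppers in the primary analysis.** Let k be the number who respond at S + 48 but have no qualifying week-96 result (k is an assumption). The estimate moves from 10/40 to (10 − k)/40, which is 1/40 = 2.5 points each:
- k = 0: 25.0% (12.7% to 41.2%)
- k = 1: 22.5% (10.8% to 38.5%)
- k = 2: 20.0% (9.1% to 35.6%)
- k = 4: 15.0% (5.7% to 29.8%)

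If such a participant is instead assessed at week 96 after a week-36 stop, the result reflects 96 − 36 = 60 weeks off treatment rather than 48.

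**The case against.** The strongest reply is that the gap is one of wording with little effect on results. The synopsis promises follow-up of every participant to week 96. The only groups with an explicit schedule that ends sooner are non-response and breakthrough stoppers, who fail the primary analysis under either anchor. There may be few of them: section 5.2.1 cites a mean fall of 5 to 6 logs with entecavir in treatment-naïve patients, and section 5.2.4 cites 0.2% resistance at one year. Weighting and imputation use earlier visits, and HBV DNA is measured at every one. Section 8.2 itself says these methods lack power in a study of this size.

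Most of this stands, and it rules out several stronger readings that a reader might infer:
- *That all early stoppers count as missing at week 96.* The documents imply this only for non-response and breakthrough. For the other reasons it is possible but not stated.
- *That every early stopper shifts the primary estimate by 2.5 points.* Only one who responds at S + 48 without a qualifying week-96 result does so; a non-responder shifts it by 0.
- *That all three sensitivity analyses lean upward.* LOCF would use the visit 48 weeks after stopping.
- *That 27.8% or 31.3% is what the planned weighting would give.* Both ignore the weights, and the documents support no particular number of stoppers. The 6% to 9% discontinuation in section 5.3.3 concerns peginterferon, and under 7.5.4 entecavir then continues.

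The reply does not remove the defect. The synopsis conflicts with 6.9.3 and 6.10.3 rather than settling them, and nothing in 8.2 exempts declared failures from being treated as missing.

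**Conclusion.** The concern holds in a limited form. The current text gives the primary efficacy endpoint two anchors that differ for anyone who stops all therapy before week 48, and no rule chooses between them. Read as written, the weighting and imputation analyses would treat participants whom the protocol already calls failures as missing, so those two analyses can be biased upward. The primary analysis is unaffected for these participants, and LOCF probably is too.

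The size of the bias cannot be estimated from the documents. The figure of 27.8% against 25.0% assumes 10 responders, 4 such stoppers and weights that carry no outcome information; with informative weights the gap could nearly vanish. For toxicity, decompensation, ALT flare, refusal and pregnancy, the effect on the primary estimate is 2.5 points for each participant who responds 48 weeks after stopping but has no qualifying week-96 result. The documents give no expected number of these. This is an inexpensive correction worth making before analysis; it does not show that the primary result is wrong.

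**What to change.** - In 2.2.2, 8.1.1, 8.2 and 8.3, use one anchor: 48 weeks after the last dose of the last study drug, which is week 96 for participants treated for 48 weeks.
- Reconcile the synopsis statement on follow-up to week 96 with 6.9.3 and 6.10.3. For each other stopping reason, state which already planned visit supplies the endpoint.
- Score participants who meet 6.9 or 6.10 as non-responders in the primary analysis and in every sensitivity analysis.
- Treat as missing only other participants who lack the endpoint visit.

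The cost is wording. A reader might infer that all the needed visits already exist, but that is shown only for participants stopped under 6.9 or 6.10. Some who stop for other reasons have no explicitly scheduled visit 48 weeks after stopping; they may remain missing and so count as failures in the primary analysis.
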